With regards to adverse events (AEs), there was one patient who died within 7 days of study enrollment and two patients who died within 28 days. Other serious adverse events (SAEs) included endotracheal intubation, a below the knee amputation, chest tube placement for a pleural effusion, and emergency surgery for a misplaced gastrostomy tube. None of the SAEs were deemed to be related to study interventions. Adverse events included hyperglycemia, anemia, elevated AST, elevated triglycerides, elevated bilirubin, intravenous catheter infiltration, and elevated PT/INR values. The most common possibly related AEs included elevated liver function tests. No patients met the prespecified criteria for a dose limiting toxicity. Please see full DSM report. At the recommendation of the DSM, the Phase I study was concluded at a maximal dose of 1.6g/kg and did not proceed to 1.8 g/kg given the low likelihood of added benefit of dose escalation to 1.8g/kg body weight and feasibility issues with line infiltration given prolonged drug infusions with increasing doses. The DSM unanimously recommended proceeding to the Phase II study with the design outlined below.

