Standard of Care Treatment: All patients will be treated in the ED or in a monitored inpatient setting at UF JAX. All patients will undergo standard emergent interventions and treatment with institutional sepsis protocols, an institutional standard of care and comprised of early, evidence-based treatment of sepsis that is utilized hospital-wide. It has been shown to result in improved outcomes.(Croft et al., 2014; Guirgis, Jones, et al., 2017)

4.5 Investigational Treatment. Within 24 hours of sepsis recognition, eligible patients (or their legal representatives in the case of inability to consent) will be approached for study enrollment. If a LAR is utilized and the subject gains the capacity to consent, the subject will be re-consented. After informed consent the following study procedures will be followed:

A. Treatment. The LIE is Smoflipid (20% lipid emulsion for injection; Fresenius Kabi), which contains soybean oil, MCTs, olive oil, and fish oil in a 30:30:25:15 ratio. Smoflipid also contains 0.163 to 0.225 mg/mL of all-rac- α -tocopherol. Initial infusion rate of LIE will occur at a rate of 0.5 mL/min for the first 30 minutes. If tolerated, the infusion will proceed at the maximum FDA approved rate of 0.11g/kg/hr, and not to exceed 0.5 mL/kg/hr. The proposed dose of LIE is based on current manufacturer recommended dosing for nutritional purposes for this specific drug. The approved dose range is 1 to 2 g/kg/day, and not to exceed 2.5 g/kg/day. Since this is a pilot study, and because the lipid emulsion appears white and will be visible to the treatment team, the study will not be blinded. All infusion bags and hospital equipment that will be used for administration of LIE are standard use in the hospital and approved by the FDA, and non-PVC tubing and a 1.2 micron in-line filter will be used. All study treatments will be administered either via an existing central venous catheter or via a single lumen peripheral intravenous catheter. This approved method of administration has been shown to be safe.

B. Weight-based dosing. Dosing will be based on actual body weight in kilograms, except in cases of morbid obesity defined as actual weight (AW) > 200% ideal body weight (IBW). For morbidly obese patients, adjusted body weight (AdjBW) will be used for Smoflipid dosing according to the following formula:

$$\text{AdjBW} = \text{IBW} + 0.4(\text{ABW} - \text{IBW}).$$

Ideal body weight in (kg) will be calculated as follows.

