D. SOFA Score. Assessment will occur at enrollment and 48h later as well as 7 days later to determine change in SOFA score over time as well as serum lactate. Necessary labs will be paid for by the study unless already ordered by the treating team.

E. Future Testing. In addition, the patient or LAR will be presented with a consent for a biobank study for future testing should they choose to participate. The biobank, Emergency Medicine Research Data and Tissue Bank, has previously been approved by the UF Jacksonville IRB and has been assigned study number IRB201601987.

Stool Sampling. A stool sample will be collected for determining lipid absorption within 24 hours of each time point when available (enrollment, 48h, 7 days) utilizing standard of care procedures by nursing and medical technicians.

4.7 Comparison Group. Phase II of this study will randomize patients to receive one of three doses of LIE or no investigational drug. The control group will receive all standard treatments mandated by the institutional Sepsis Alert protocol. For purposes of statistical outcomes analysis, the control group will be the comparison group.

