1. Hypersensitivity reactions resulting in facial, head or neck swelling, airway compromise, shortness of breath or hypoxia will result in cessation of drug infusion on a study patient. No patients experience allergic drug reactions will continue to receive or receive additional doses of study drug.

Dose Escalation and Dose-Limiting Toxicities include:

2. Respiratory distress or hypoxia occurring very soon after initiation of study drug.
3. Fat Overload or Hypertriglyceridemia (> 1000 mg/dL)
4. Parenteral nutrition associated liver disease or hepatitis characterized by a marked elevation of liver function tests or total bilirubin.

For AEs that do not meet criteria of SAEs or deemed to be "not related" or "possibly related" the PI and Co-Investigators will make decisions regarding management based on the clinical scenario (See DSMP Adverse Events Monitoring Section I).

"Hypersensitivity reactions resulting in facial, head or neck swelling, airway compromise" as detailed in the AE and SAE monitoring section. Though considered SAEs, these will not be considered dose limiting toxicities as allergic reactions are not dose-related. Therefore dose escalation in the Phase I study can continue even if a patient experiences a hypersensitivity reaction. Hypersensitivity reactions, when severe as defined above, will however result in stopping of the study drug.

F. Patient Bedside Monitoring.

- Only patients admitted to a monitored inpatient setting or ICU an ICU setting will be enrolled in the study to ensure adequate monitoring during and after drug infusion.
- Laboratory monitoring will occur under the supervision of the study pharmacist or nutritionist with experience using the proposed LIE. The following laboratory measures will be monitored for the first 48

hours: serum triglycerides, fluid and electrolyte status, blood glucose, liver and kidney function, blood count including platelets, and coagulation parameters.

- Bedside nurse monitoring will occur for the first hour of drug infusion on day 1 of the study. Nurse monitoring will include monitoring for all of the following: tachypnea, dyspnea, hypoxia, bronchospasm, tachycardia, hypotension, cyanosis, vomiting, nausea, headache, sweating, dizziness, altered mentation, flushing, rash, urticaria, erythema, pyrexia, or chills. Vascular access will also be monitored for thrombophlebitis, erythema, pain.

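### Section 4.5 A sets a maintenance rate (0.11 g/kg/hr, or 0.55 mL/kg/hr) that its own 0.5 mL/kg/hr cap forbids, and the fixed starting rate is too fast for light patients (minor)

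*Combined protocol and SAP*

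**What the plan says.** Section 4.5 A (Treatment) describes the product as a "20% lipid emulsion for injection". The infusion has two steps. The first is fixed and does not depend on weight: "Initial infusion rate of LIE will occur at a rate of 0.5 mL/min for the first 30 minutes". The second depends on weight and carries two limits in different units: "If tolerated, the infusion will proceed at the maximum FDA approved rate of 0.11g/kg/hr, and not to exceed 0.5 mL/kg/hr". The same paragraph gives the daily limits: "The approved dose range is 1 to 2 g/kg/day, and not to exceed 2.5 g/kg/day".

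Section 4.5 B sets the weight to use: "Dosing will be based on actual body weight in kilograms, except in cases of morbid obesity", where an adjusted weight replaces it. The entry criteria in section 4.3 contain no minimum weight. Section 4.7 says that Phase II will "randomize patients to receive one of three doses of LIE or no investigational drug"; the three doses are not in the visible text.

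**The concern.** The two limits on the maintenance rate look like one rate written in two units, but they do not convert into each other at the stated concentration. A pharmacist who writes the order from the g/kg/hr figure programs a faster pump than one who writes it from the mL/kg/hr figure, and each can point to the same sentence. No other section reconciles the two.

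The first 30 minutes raise a separate point. The words introducing the second step make the start a tolerance test. A test step should be no faster than the rate it tests, yet a fixed mL/min rate is a higher weight-based rate in a lighter patient.

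What is at stake is how an operative dosing rule is carried out in critically ill patients. The protocol treats early respiratory reactions and high triglycerides as toxicities of concern (section 4.9 E). The total dose and the statistical analysis are not at stake.

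**Working it through.** **Inputs, all from section 4.5 A**

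- Concentration: 20%, read as 0.20 g/mL (an assumption, varied below)
- Start: 0.5 mL/min for 30 minutes
- Maintenance: 0.11 g/kg/hr, capped at 0.5 mL/kg/hr

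**Maintenance rate.** Formula: mL/kg/hr = (g/kg/hr) ÷ (g/mL).

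- Instructed rate: 0.11 ÷ 0.20 = 0.55 mL/kg/hr
- Cap: 0.5 × 0.20 = 0.10 g/kg/hr
- Ratio: 0.55 ÷ 0.50 = 1.10, at every weight
- At 70 kg: 0.55 × 70 = 38.5 mL/hr against 0.5 × 70 = 35 mL/hr

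The two printed figures therefore do not reproduce each other. If 20% were by weight, with an assumed density of about 0.99 (0.198 g/mL), the instructed rate would be 0.11 ÷ 0.198 = 0.556 mL/kg/hr and the conflict would remain. The limits agree only at 0.11 ÷ 0.5 = 0.22 g/mL, a 22% emulsion.

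**Start rate.** 0.5 × 60 = 30 mL/hr, and 30 × 0.20 = 6 g/hr.

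- Weight below which the start exceeds 0.11 g/kg/hr: 6 ÷ 0.11 = 54.5 kg
- Weight below which it exceeds 0.5 mL/kg/hr: 30 ÷ 0.5 = 60 kg

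| Dosing weight | Start, g/kg/hr (6 ÷ kg) | Against 0.11 g/kg/hr | Start, mL/hr | Capped maintenance, mL/hr (0.5 × kg) |
|---|---|---|---|---|
| 45 kg | 0.133 | 21% over | 30 | 22.5 |
| 50 kg | 0.120 | 9% over | 30 | 25 |
| 60 kg | 0.100 | below | 30 | 30 |
| 70 kg | 0.086 | below | 30 | 35 |

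**Excess lipid during the start.** The start delivers 6 × 0.5 = 3.0 g. At 0.11 g/kg/hr the same 30 minutes would deliver:

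- 50 kg: 0.11 × 50 × 0.5 = 2.75 g, an excess of 0.25 g
- 45 kg: 0.11 × 45 × 0.5 = 2.475 g, an excess of 0.525 g

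If one infusion is taken as 1 to 2 g/kg (the approved daily range, an assumption because the Phase II doses are not visible), the excess is 0.25 ÷ 100 to 0.25 ÷ 50, or 0.25% to 0.5% of the dose, at 50 kg. At 45 kg it is 0.525 ÷ 90 to 0.525 ÷ 45, or 0.6% to 1.2%.

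**Duration, ignoring the start.** Formula: dose ÷ rate.

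| Dose as one infusion | At 0.11 g/kg/hr | At 0.10 g/kg/hr | Difference |
|---|---|---|---|
| 1 g/kg | 9.1 h | 10.0 h | 0.9 h |
| 1.6 g/kg (top Phase I dose) | 14.5 h | 16.0 h | 1.5 h |
| 2 g/kg | 18.2 h | 20.0 h | 1.8 h |

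**The case against.** The maintenance sentence can be read so that it resolves itself: a rate followed by a ceiling normally means that the ceiling governs, so the infusion runs at 0.5 mL/kg/hr. The protocol does not say that one figure is the conversion of the other. On its own terms neither reading is unsafe, because it describes 0.11 g/kg/hr as the approved maximum. This reading yields a workable order, but it leaves the sentence instructing a rate that its cap never permits, and the reader must convert units to find that out.

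On the start, both limits are written for the period after 30 minutes. Whether they also bind the first step depends on the product label, which the documents do not reproduce. That stands, so going over 0.11 g/kg/hr below 54.5 kg cannot be called a breach of an applicable limit. The step-down below 60 kg needs no label: at 50 kg the tolerance step runs at 30 mL/hr and the full rate is at most 25 mL/hr.

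There are also safeguards. Section 4.9 F provides that "Bedside nurse monitoring will occur for the first hour of drug infusion on day 1 of the study", which covers the whole start on that day, and it adds laboratory monitoring including triglycerides for 48 hours. Section 4.9 E stops the drug for severe related reactions. The Phase I summary reports no dose-limiting toxicity up to 1.6 g/kg. These points limit the harm and support a minor rating. They do not tell staff which rate to program. The nurse monitoring is specified for day 1 only, although the adverse event reporting section describes two infusions; whether the slow start is repeated on day 2 is not stated.

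**Conclusion.** The concern holds and is minor. As written, the instructed maintenance rate is 10% above its own cap at every weight. This rests only on reading 20% as 0.20 g/mL, and the weight-by-weight reading does not rescue it. The fixed start exceeds 0.11 g/kg/hr below 54.5 kg and is faster than the capped follow-on rate below 60 kg. Whether the start breaks an applicable limit is for the label to settle.

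The practical effect is a difference of 0.9 to 1.8 hours in infusion time for 1 to 2 g/kg and, in light patients, a fraction of a gram of extra lipid in the first 30 minutes. The documents give no weight distribution, so the number of the 24 treated patients below either threshold is unknown and could be zero.

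**What to change.** State one maintenance rate, in both units. The choice consistent with both printed limits is 0.5 mL/kg/hr (0.10 g/kg/hr). If the study pharmacist confirms from the label that 0.11 g/kg/hr is the intended limit, keep it and correct the cap to 0.55 mL/kg/hr. Set the first 30 minutes at the lower of 0.5 mL/min and that weight-based maximum for the patient's dosing weight.

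The cost is a one-sentence correction and a check of the order set. Running at 0.5 mL/kg/hr makes an infusion about 10% longer than at 0.11 g/kg/hr. That is not free, since the Phase I summary cites "feasibility issues with line infiltration given prolonged drug infusions with increasing doses" among the reasons for stopping escalation. Even so, 2 g/kg would finish in about 20 hours.

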4.8 Efficacy Endpoints

A. Primary Endpoints

- Delta (48h - enrollment) serum total cholesterol of 0 to 5 mg/dL

B. Secondary Endpoints

- Lipid oxidation (HDL inflammatory index)
- HDL function (cholesterol efflux capacity)
- Change in SOFA score over the first 48h and 7 days
- In-hospital mortality
- Change in cholesterol level from enrollment to 7 days

4.9 Study Procedures.

A. Randomization

Phase II of this study/trial will use an adaptive design. As the study progresses, the dose of the study drug that proves least efficacious for stabilizing cholesterol levels will be dropped. For the first 24 patients, patients will be randomized to receive one of three doses of the study drug, or no drug (active control). The first 24 patients will be randomized using the following allocations: 4:4:4:12. From the first 24 patients, we will select the two doses that have the best performance in the primary endpoint, Delta (48h - enrollment) serum total cholesterol of 0 to 5 mg/dL, among the ones that are acceptable in safety. We will also evaluate Delta SOFA score at 48 hours (organ failure score, from 48h-enrollment) as well as Delta 7 days for serum total cholesterol (7 day – enrollment) to select the two most efficacious doses. For the last 24 patients in the study, patients will be randomized to receive one of the two most efficacious doses of study drug based on results from the first 24 patients in the following manner: 6:6:12, or no drug (active control). The overall study groups will include 24

patients in the experimental arm and 24 patients in the control arm as originally designed. The study will employ a permuted blocked randomization technique. Permuted blocked randomization has several advantages in that it supports group balance at the end of the trial and it supports continuous balance during trial progression by assuring that sequential patients are distributed equally between groups. The study statistician will generate the randomization sequence that will be stored in REDCap and accessed by the study coordinators at the time of patient enrollment.

B. Blinding. Because this is a pilot study, and because the lipid emulsion appears white and will be visible to the treatment team, the study will not be blinded. Data abstractors will, however, be blinded to the treatment effect. As the treatment effects are objective measurements (lipid levels, SOFA score, etc.) the likelihood of bias is low.

C. Drug Accountability. The drug for this study will be supplied by the hospital pharmacy and paid for by the study. A SOP will be used to track lot numbers of LIE administered.

D. Sample Size. Our preliminary data suggests that with proposed enrollment criteria, patients experienced an average decrease of 17 mg/dL (SD = 23) in cholesterol at 48 hours. If the treatment group can stop the decline or increase by 2 mg/dL in cholesterol, which correspond to between group difference with Cohen's effect size of 0.74 or 0.83. Then, at a significance level of 0.05, 24 patients in each arm (N = 48) will be able to detect the difference at 71% or 80% power, respectively. Recruitment feasibility: Based upon extensive prior work by the senior PI at the research hospital, we expect to enroll approximately 2 patients/month and all study patients within 4 years.

E. Safety Monitoring. This study will employ a Data Safety Monitoring Plan (see full plan at end of study protocol) that includes a primary physician safety monitor (not a co-investigator) who will have expertise in critical care and the study drug. The DSM plan also includes a second safety monitor (not a co-investigator) who is a clinical trialist who also has experience in critical care. The third member of the DSM plan is a biostatistician with experience in clinical trials and critical care studies and with prior DSMB experience. All DSM meetings to evaluate for safety will be coordinated by the study monitor. Since the Phase I study has been completed (10 patients) and the DSM has approved the start of Phase II, subsequent meetings will occur after the thirtieth, and forty fifth patients are enrolled and after study completion. The DSM will have the authority to make one of three written recommendations to the study PI after each meeting: suspend the study, continue the study without restriction, or continue the study with contingency on review of additional data regarding adverse events, adjustments to the protocol, or individual patient's clinical history.

AE and SAE Monitoring

Any reaction deemed to be severe (as listed below) and related to the drug infusion while it is being infused, will result in discontinuation of the study drug after discussion with the PI. Potential expected AEs include the following:

1. Hypersensitivity reactions resulting in facial, head or neck swelling, airway compromise, shortness of breath or hypoxia will result in cessation of drug infusion on a study patient. No patients experience allergic drug reactions will continue to receive or receive additional doses of study drug.

Dose Escalation and Dose-Limiting Toxicities include:

2. Respiratory distress or hypoxia occurring very soon after initiation of study drug.
3. Fat Overload or Hypertriglyceridemia (> 1000 mg/dL)
4. Parenteral nutrition associated liver disease or hepatitis characterized by a marked elevation of liver function tests or total bilirubin.

For AEs that do not meet criteria of SAEs or deemed to be "not related" or "possibly related" the PI and Co-Investigators will make decisions regarding management based on the clinical scenario (See DSMP Adverse Events Monitoring Section I).

"Hypersensitivity reactions resulting in facial, head or neck swelling, airway compromise" as detailed in the AE and SAE monitoring section. Though considered SAEs, these will not be considered dose limiting toxicities as allergic reactions are not dose-related. Therefore dose escalation in the Phase I study can continue even if a patient experiences a hypersensitivity reaction. Hypersensitivity reactions, when severe as defined above, will however result in stopping of the study drug.

F. Patient Bedside Monitoring.

- Only patients admitted to a monitored inpatient setting or ICU an ICU setting will be enrolled in the study to ensure adequate monitoring during and after drug infusion.
- Laboratory monitoring will occur under the supervision of the study pharmacist or nutritionist with experience using the proposed LIE. The following laboratory measures will be monitored for the first 48

hours: serum triglycerides, fluid and electrolyte status, blood glucose, liver and kidney function, blood count including platelets, and coagulation parameters.

- Bedside nurse monitoring will occur for the first hour of drug infusion on day 1 of the study. Nurse monitoring will include monitoring for all of the following: tachypnea, dyspnea, hypoxia, bronchospasm, tachycardia, hypotension, cyanosis, vomiting, nausea, headache, sweating, dizziness, altered mentation, flushing, rash, urticaria, erythema, pyrexia, or chills. Vascular access will also be monitored for thrombophlebitis, erythema, pain.

Safety assessments will consist of monitoring and reporting adverse events (AEs) and serious adverse events (SAEs) that are considered related to LIE, all events of death, and any study specific issue of concern.

Adverse Events

An AE is any unfavorable and unintended sign, symptom, or disease temporally associated with the use of LIE in this study. The study-specific definition of “temporally related” includes up to twelve hours after discontinuation of LIE infusion.

This includes the following:

- AEs not previously observed in the subject that emerge during the protocol-specified AE reporting period.
- If applicable, AEs that occur prior to assignment of study treatment associated with medication washout, no treatment run-in, or other protocol-mandated intervention.
- Preexisting medical conditions (other than the condition being studied) judged by the investigator to have worsened in severity or frequency or changed in character during the protocol-specified AE reporting period.
- Laboratory values that are abnormal to a degree such that the value falls into the range specified as abnormal by local standards, and the abnormality leads to specific medical corrective action.

Serious Adverse Events

An AE should be classified as an SAE if:

- It results in death (i.e., the AE actually causes or leads to death).
- It is life threatening (i.e., the AE, in the view of the investigator, places the subject at immediate risk of death. It does not include an AE that, had it occurred in a more severe form, might have caused death.).
- It requires or prolongs inpatient hospitalization.
- It results in persistent or significant disability/incapacity (i.e., the AE results in substantial disruption of the subject's ability to conduct normal life functions).
- It results in a congenital anomaly/birth defect in a neonate/infant born to a mother exposed to the investigational product.
- It is considered a significant medical event by the investigator based on medical judgment (e.g., may jeopardize the subject or may require medical/surgical intervention to prevent one of the outcomes listed above).

Methods and Timing for Assessing AND Recording Safety variables

The investigator is responsible for ensuring that all AEs and SAEs that are observed or reported during the study are collected and reported to the FDA, appropriate IRB(s) in accordance with CFR 312.32 (IND Safety Reports).

Adverse Event Reporting Period

